My signature below verifies that I have read and agree to this protocol. I am aware of my responsibilities as an investigator under the current ICH GCP guidelines, the Declaration of Helsinki, United States of America (US) Food and Drug Administration (FDA) Code of Federal Regulations (CFRs) and state and local regulations and applicable laws and regulations of the country of the study site for which I am responsible. I agree to conduct the study according to these regulations.

I have read this protocol in its entirety and agree to conduct this study accordingly. Any changes in procedure will only be made if necessary, to protect the safety, rights, and welfare of study participants.

I agree to conduct in person and/or to supervise staff assigned to specific study responsibilities. I will ensure that all staff who assist me in the conduct of the study have access to the protocol and all pertinent information. I will ensure that all assigned staff are trained and qualified and are fully informed of their responsibilities regarding the conduct of the study.

I agree to abide by the terms of the confidentiality disclosure agreement and/or contract with the sponsor and/or its representatives.

Site Principal Investigator:		
	Principal Investigator Name (print)	Title (print)
	Principal Investigator Signature	Date (DDMMMYYYY)

PROTOCOL SYNOPSIS

Name of Sponsor/Company: Emergent Travel Health Inc.

Name of Investigational Product: PXVX0317

Name of Active Ingredient(s): Chikungunya virus virus-like particle (CHIKV VLP)

Protocol Number: EBSI-CV-317-004

Title of Study: A Phase 3 Safety, Immunogenicity, and Lot-Consistency Trial of the VLP-Based Chikungunya Vaccine PXVX0317 in Healthy Adults and Adolescents

Study Centers: Multicenter, up to 50 sites in the US

Study Duration for One Participant: 7 months **Estimated Study Duration:** ~12 months Phase of Development: 3

Coprimary Objectives:

- To evaluate the safety of PXVX0317 in healthy adult and adolescent participants 12 to <65 years of age.
- To compare the anti-CHIKV serum neutralizing antibody (SNA) response to PXVX0317 and placebo at Day 22, as measured by geometric mean titer (GMT) and clinically relevant difference in seroresponse rate (PXVX0317 minus placebo).

Note: Seroresponse rate (considered the presumptive seroprotection rate) is defined as the percentage of participants who achieve an anti-CHIKV SNA See Section 6.1 for assay description.

• To demonstrate the consistency of the anti-CHIKV SNA response across three consecutively manufactured lots of PXVX0317 at Day 22 as measured by GMT.

Secondary Objectives:

- To compare the anti-CHIKV SNA response to PXVX0317 and placebo at Day 15, Day 183, and Day 8, as measured by GMT and seroresponse rate.
- To compare the anti-CHIKV SNA response to PXVX0317 and placebo in participants 12 to <18 years of age, participants 18 to <46 years of age, and participants 46 to <65 years of age as measured by GMT and seroresponse rate.

Exploratory Objective:

• To evaluate anti-CHIKV SNA response across three consecutively manufactured lots of PXVX0317 as measured by seroresponse rate for each lot at Day 22 in participants 18 to <46 years of age.

Methodology/Study Design:

This is a phase 3, randomized, placebo-controlled, double-blind, parallel-group design with four treatment groups. Participants will be randomized in a 2:2:2:1 ratio within each age stratum (12 to <18, 18 to <46, and 46 to <65) to receive one of three consecutively manufactured lots of PXVX0317 or placebo. With 3150 participants enrolled, the treatment group totals are estimated as follows:

- Group 1- PXVX0317 lot A: n=900
- Group 2- PXVX0317 lot B: n=900
- Group 3- PXVX0317 lot C: n=900
- Group 4- Placebo: n=450

A nested lot consistency substudy will be performed in adult participants 18 to <46 years of age in the PXVX0317 treatment groups (lot A, lot B, and lot C).

Procedures and Assessments:

Study procedures and assessments will occur at: Screening (Visit 1), to occur no more than 30 days prior to Day 1 of investigational product (IP) administration; Day 1 (Visit 2, baseline, randomization, and administration of IP); Day 8 (Visit 3); Day 15 (Visit 4); Day 22 (Visit 5); Day 29 (Visit 6, via telephone contact); Day 92 (Visit 7, via telephone contact); Day 183 (Visit 8, End of Study) or; Early Discontinuation Visit. The per participant estimated total study duration is 212 days.

Solicited adverse events (AEs collected from IP administration on Day 1 through Day 8) will consist of local (injection site pain, redness, and swelling) and systemic (fever, chills, fatigue, headache, myalgia, arthralgia, and nausea) reactions. Unsolicited AEs will be collected from Day 1 through Day 29. Serious adverse events (SAEs), adverse events of special interest (AESI), and medically attended adverse events (MAAE) will be collected from Day 1 through to the Day 183 End of Study Visit. An independent Safety Monitoring Committee (SMC) will review aggregated, blinded safety data after the 300th enrolled participant passes Day 29, and again after the last enrolled participant passes Day 29.

The induction of the humoral immune response (immunogenicity) by PXVX0317 vaccine, specifically anti-CHIKV SNA titers, will be measured by a bioluminescence assay developed by the sponsor that uses a modified version of CHIKV containing a reporter gene that expresses a luciferase protein (CHIKV-luc) in infected Vero cells *in vitro*. Reduction of luciferase activity (ie, reduced bioluminescence) occurs in infected cultures of cells following treatment of CHIKV-luc with test serum containing anti-CHIKV SNA. The quantitation of reporter gene expression, a correlate of the level of virus infection of cells, is determined by detection of luciferase using a microplate luminometer. The anti-CHIKV SNA titer 80 (NT₈₀) is the reciprocal of the serum dilution that provides 80% protection of Vero cells from CHIKV-luc infection or an 80% reduction of luciferase activity compared to virus only control.

The levels of anti-CHIKV SNA will be determined for time points up to 182 days after dosing (Day 183 End of Study Visit).

Number of Participants (Planned): At least 3150

Study Population: Healthy adult and adolescent participants 12 to <65 years of age

Criteria for Study Participation

Inclusion Criteria:

Participants must meet all the following criteria to be enrolled:

- 1. Able and willing to provide informed consent (and assent, as applicable) voluntarily signed by participant (and guardian, as applicable).
- 2. Males or females, 12 to <65 years of age.
- 3. Generally healthy, in the opinion of the investigator, based on medical history, physical examination, and screening laboratory assessments.
- 4. Women who are either:
 - i. Not of childbearing potential (CBP): pre-menarche, surgically sterile (at least six weeks post bilateral tubal ligation, bilateral oophorectomy or hysterectomy), or postmenopausal (defined as a history of ≥12 consecutive months without menses prior to randomization in the absence of other pathologic or physiologic causes, following cessation of exogenous sex-hormonal treatment).

or:

ii. Meeting all the below criteria:

- Negative serum pregnancy test at Screening Visit
- Negative urine pregnancy test immediately prior to dosing at Day 1
- Use one of these acceptable methods of contraception (if women of CBP) for the duration of participation:
 - Hormonal contraceptives (eg, implants, pills, patches) initiated ≥30 days prior to dosing
 - Intrauterine device (IUD) inserted \geq 30 days prior to dosing
 - Double barrier type of birth control (male condom with female diaphragm, male condom with cervical cap)
 - Abstinence is acceptable **only for adolescents** (12 to <18 years old) who are not sexually active.

Note: See Section 3.3.7 for this study's list of acceptable method of contraception.

Note: Contraception requirements do not apply for participants in exclusively same-sex relationships and these participants should have no plans to become pregnant by any other means for the duration of the study.

Exclusion Criteria:

Participants who meet **any** of the following criteria **cannot** be enrolled:

- 1. Currently pregnant, breastfeeding, or planning to become pregnant during the study.
- 2. Body Mass Index (BMI) \geq 35 kg/m².
- 3. Positive laboratory evidence of current infection with human immunodeficiency virus (HIV-1, HIV-2), hepatitis C virus (HCV) or hepatitis B virus (HBV).
- 4. History of severe allergic reaction or anaphylaxis to any component of the IP.
- 5. History of any known congenital or acquired immunodeficiency that could impact response to vaccination (eg, leukemia, lymphoma, generalized malignancy, functional or anatomic asplenia, alcoholic cirrhosis).
- Prior receipt or anticipated use of systemic immunomodulatory or immunosuppressive medications from six months prior to screening through Day 22. Note: For systemic corticosteroids, use at a dose or equivalent dose of 20 mg of prednisone daily for 14 days or more within three months of screening through Day 22 is exclusionary. The use of inhaled, intranasal, topical, ocular, or intraocular steroids is allowed.
- 7. Receipt or anticipated receipt of blood or blood-derived products from 90 days prior to screening through Day 22.
- 8. Acute disease within the last 14 days (participants with an acute mild febrile illness can be considered for a deferral of vaccination two weeks after the illness has resolved and treatment has been completed).
- 9. Clinically significant cardiac, pulmonary, rheumatologic, or other chronic disease, in the opinion of the investigator. This may include chronic illness requiring hospitalization in the last 30 days prior to screening.
- 10. Enrollment in an interventional study and/or receipt of another investigational product from 30 days prior to screening through the duration of study participation.
- 11. Receipt or anticipated receipt of any vaccine from 30 days prior to Day 1 through Day 22.
- 12. Evidence of substance abuse that, in the opinion of the investigator, could adversely impact the participant's participation or the conduct of the study.

- 13. Prior receipt of an investigational CHIKV vaccine/product.
- 14. Any other medical condition that, in the opinion of the investigator, could adversely impact the participant's participation or the conduct of the study.

Investigational Product, Dosage, and Mode of Administration:

PXVX0317 vaccine is comprised of CHIKV VLP 40 μg, aluminum hydroxide (Alhydrogel[®]) 2% adjuvant, and formulation buffer supplied as a single dose of 0.8 mL in a pre-filled syringe administered via intramuscular (IM) injection in the deltoid muscle.

Reference Therapy, Dosage and Mode of Administration:

Placebo is comprised of formulation buffer supplied as a single dose of 0.8 mL in a pre-filled syringe administered via IM injection in the deltoid muscle.

Criteria for Evaluation

Primary Endpoints:

Safety Endpoints:

- Incidence of solicited AEs through Day 8 for PXVX0317 and placebo.
- Incidence of unsolicited AEs through Day 29 for PXVX0317 and placebo.
- Incidence of AESI, MAAEs, and SAEs, through Day 183 for PXVX0317 and placebo.

Coprimary Immunogenicity Endpoints:

• Difference in anti-CHIKV SNA seroresponse rate (PXVX0317 minus placebo) and associated 95% confidence interval (CI) at Day 22.

Note: Seroresponse rate (considered the presumptive seroprotection rate) is defined as the percentage of participants who achieve an anti-CHIKV SNA See Section 6.1 for assay description. See Section 8.6 for immunogenicity analysis details and Section 8.6.2.5 for success criteria and multiplicity controls.

- Anti-CHIKV SNA GMT and associated 95% CIs at Day 22 for PXVX0317 and placebo.
- Anti-CHIKV SNA GMT ratio between all three pairs of PXVX0317 lots (A:B, A:C, B:C) (adults 18 to <46 years of age) at Day 22.

Secondary Endpoints:

• Key Secondary Endpoints: Difference in anti-CHIKV SNA seroresponse rate (PXVX0317 minus placebo) with associated 95% CIs at Day 15, Day 183, and Day 8, in that order (see Section 8.6.2.5).

- Anti-CHIKV SNA GMTs by study arm with associated 95% CIs at Day 8, Day 15, and Day 183.
- Geometric mean fold increase (GMFI) from Day 1 to subsequent collection time points.
- Number and percentage of participants with an anti-CHIKV SNA titer ≥ 15 and 4-fold rise over baseline.

Exploratory Endpoints:

• Anti-CHIKV SNA seroresponse rate difference with associated 95% CIs for each pair of PXVX0317 lots (A minus B, A minus C, B minus C) (adults 18 to <46 years of age) at Day 22.

Statistical Methods

Sample Size Considerations:

The primary statistical comparison between the PXVX0317 and placebo treatment groups is based on difference between treatment groups in seroresponse rate (proportion of participants with CHIKV-luc assay anti-CHIKV SNA NT₈₀ [human SNA assay] at Day 22.

Based on the data from the phase 2 study (protocol PXVX-CV-317-001), the seroresponse rate for PXVX0317 vaccine is expected to be approximately vs <5% for the placebo participants. With an assumed 10% rate of non-evaluable participants, the power to show superiority over placebo with 2430 PXVX0317 vaccine and 405 placebo evaluable participants is >99.9% for the combined age groups. The power is 99% for each of the smaller 12 to <18 and 46 to <65 age groups with samples sizes of 210 vs 35 evaluable participants (PXVX0317: placebo).

The difference in seroresponse rate between PXVX0317 and placebo groups that is considered clinically relevant is **100**. With 2430 PXVX0317-treated participants and a target seroresponse rate of **100** vs a rate of 0% for placebo, the width of a two-sided 95% CI would be $\pm 1.2\%$. The difference in seroresponse rate must be above **100** for the lower bound of the 95% CI for the difference to be **100**.

The second consideration for sizing the study is ensuring adequate power for the lot consistency equivalence intervals testing immunogenicity at Day 22, as measured by human SNA assay GMT ratios between all three pairs of consecutively manufactured PXVX0317 lots (A:B, A:C, B:C) in the 18 to <46 years of age stratum for the immunogenicity evaluable population (IEP). For all three pairwise GMT ratios, the two-sided 95% CI must fall within [0.667, 1.5] for the lots to be considered equivalent.

On the log_{10} scale, two one-sided equivalence tests have 95% power to reject the null hypothesis that the difference in mean titers between lots is below -0.176 or above 0.176 in favor of an alternative hypothesis of equivalence when the expected difference in log_{10}

means is 0, the common standard deviation (SD) is 0.455, each test is at the 2.5% level and the sample size in each lot is 207. The SD estimate is based on the upper bound of an 80% CI on the SD on the log_{10} scale observed in the human SNA assay on samples collected 4 weeks after participants were treated with a single dose of PXVX0317. To be conservative, at least 1050 evaluable participants (300 participants administered PXVX0317 from each lot and 150 participants administered placebos) need to be enrolled into the 18 to <46 age group to provide adequate power for the lot consistency objective.

The final consideration for the sample size of the study is the size of the prelicensure safety database. With 2700 participants receiving any lot of PXVX0317, this study is 93.3% likely to detect at least one AE with a true frequency of $\geq 0.1\%$ (ie, "uncommon").

Analysis

Safety:

All safety analyses will be based on the safety population. The three PXVX0317 lots will be combined in the tabulations and each of the safety analyses will be summarized across all ages and repeated for three (12 to <18, 18 to <46, and 46 to <65) participant age groups. Incidences of local (ie, injection site pain, redness, and swelling) and systemic reactions (ie, fever, chills, fatigue, headache, myalgia, arthralgia, and nausea) occurring from IP administration on Day 1 through Day 8 will be summarized by maximum severity and by treatment group. Unsolicited AEs will also be summarized by maximum severity and treatment group according to Medical Dictionary of Regulatory Activities (MedDRA) by system organ class (SOC) and preferred terms (PT).

Superiority to Placebo at Day 22:

The proportion of participants in each treatment group (PXVX0317 and placebo) with seroresponse at titer will be computed, along with the two-sided 95% CI. This analysis will be primarily based the IEP and repeated for the modified intent-to-treat (mITT) population as a measure of the robustness of the findings. The significance of the treatment group difference will be assessed using a chi-square test, based on the response across all age groups combined, with an alpha=0.05. The significance of the difference in seroresponse rates between treatment groups for each age cohort will also be determined.

The difference in seroresponse rates between the two groups will be calculated, along with the 95% CI for the difference based on the Newcombe hybrid score method. The lower bound of the two-sided 95% CI on the difference in seroresponse rates between PXVX0317 and placebo must be to satisfy the primary objective to demonstrate a clinically relevant seroresponse. Differences in seroresponse rates between the two groups will be tested similarly at Days 15, 183, and 8, in that order (see Section 8.6.2.5).

Day 22 GMTs will be compared between PXVX0317 and placebo treatment groups and will be analyzed via a linear model based on a two-sided alpha=0.05. The primary model is an analysis of variance (ANOVA), with logarithmically transformed anti-CHIKV SNA titers (log₁₀) as the dependent variable and treatment group and study site as the fixed

effects in the model. The adjusted least square means and their 95% CIs calculated based on the ANOVA will be back transformed and reported as the group GMT values.

Lot Consistency:

For all three pairs of lots (A:B, A:C, and B:C), the two-sided 95% CI for the ratio of anti-CHIKV SNA GMTs at Day 22 in PXVX0317-treated participants ages 18 to <46 will be computed. The 95% CI must be contained within the [0.667; 1.5] interval for the lots to be considered equivalent. This analysis will be based on the IEP. The analyses will also be run for the mITT population as a measure of the robustness of the results.

	~				1		r	
	Screening Visit 1	Day 1 Visit 2	Day 8 Visit 3	Day 15 Visit 4	Day 22 Visit 5	Day 29 Visit 6 (Phone)	Day 92 Visit 7 (Phone)	Day 183 ¹³ Visit 8
Window (days)	Within 30 days of Day 1		-1/+3	-1/+3	-1/+3	±1	±3	-14/+7
Informed Consent/Assent	Х							
Eligibility Criteria	Х	*Х						
Medical History	X^1	*X ²						
Demography	Х							
Physical Exam	X ³	*X ⁴	X^4	X^4	X^4			X^4
Viral Marker testing (HIV-1/2, anti-HCV ⁵ , HBsAg)	Х							
Urine Toxicology ⁶	Х							
Vital Signs ⁷	Х	*X ⁸						
Pregnancy Test (female of CBP)	X ⁹	*X ¹⁰						
FSH Levels (post-menopausal female)	Х							
Randomization		*Х						
Administration of Investigational Product		Х						
Acute Observation		Х						
Solicited AEs		Х	Х					
Unsolicited AEs		Х	Х	Х	Х	Х		
SAEs		Х	Х	Х	Х	Х	Х	Х
AESI		Х	Х	Х	Х	Х	Х	Х
MAAE		Х	Х	Х	Х	Х	Х	Х
Concomitant Medications	Х	Х	Х	Х	Х	Х	X ¹¹	X^{11}
Anti-CHIKV SNA Sample		*X	X	X	X			X
e-Diary Training and Distribution of Devices ¹²		Х						
e-Diary Collection and Review			Х					

SCHEDULE OF EVENTS

*To be done prior to IP administration.

EBSI-CV-317-004, Version 5.0 20 Mar 2023

FSH = follicle stimulating hormone

¹To include presence of joint pain.

²To be updated if necessary.

³Complete physical exam.

⁴Directed physical exam, as needed.

⁵If HCV antibody is positive HCV ribonucleic acid (RNA) testing can be performed.

⁶Urine toxicology, per investigator's discretion.

⁷To include height and body weight (for BMI calculation).

⁸To be taken before and after IP administration.

⁹Serum pregnancy test.

¹⁰Urine pregnancy test.

¹¹Concomitant medications associated with SAE/AESI/MAAE only.

¹²Smart phone (e-diary), digital thermometer, and ruler.

¹³Early Discontinuation/Withdrawal Visit occurring within 7 days postvaccination, from 7 to 21 days postvaccination, or \geq 22 days postvaccination the Visit 3, Visit 5, or Visit 8 schedule will be followed respectively.

TABLE OF CONTENTS

1	BACH	KGROUND INFORMATION	23
	1.1	Name and Description of Investigational Product	23
	1.2	Chikungunya Virus and Disease Background	23
	1.3	Justification for Use of Investigational PXVX0317 Vaccine	24
	1.3.1	Summary of Animal Studies	25
	1.3.2	Summary of Findings from Clinical Studies	26
	1.3.3	Seroresponse Rate	
	1.3.4	Rationale for Dosage and Route of Administration	
	1.4	Justification for Inclusion of Adolescents 12 to <18 Years of Age	
2	STUE	Y OBJECTIVES AND PURPOSE	29
	2.1	Purpose	29
	2.2	Coprimary Objectives	29
	2.3	Secondary Objectives	
	2.4	Exploratory Objective	
3	STUE	Y DESIGN	
	3.1	Study Description	
	3.1.1	Study Centers	
	3.1.2	Number of Participants (Planned)	31
	3.1.3	Estimated Study Duration	31
	3.2	Schematic Diagram of Study Design	32
	3.3	Description of Study Assessments	
	3.3.1	Review of Eligibility Criteria	
	3.3.2	Medical History and Demography	
	3.3.3	Physical Examination	
	3.3.4	Vital Signs	
	3.3.5	Laboratory Tests	

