3.3.5 Laboratory Tests

At the Screening Visit, blood samples will be collected for serum testing for Hepatitis B surface antigen (HBsAg), HCV antibody (if HCV antibody is positive HCV RNA testing can be performed), HIV-1/HIV-2, serum pregnancy test for women of CBP, and for FSH testing for postmenopausal women (for additional information on FSH assessment see Section 3.3.7). Urine toxicology screening may be done per investigator's (or designee's) discretion at the Screening Visit. Any request to repeat testing should be discussed with the MM.

For additional information on sample collection, processing, storage, and shipment refer to the study Laboratory Manual.

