3.3.7 Pregnancy Testing and Contraception

Women of CBP will undergo a serum pregnancy test at the Screening Visit, and a urine pregnancy test prior to IP administration on Day 1. The participant must have a negative urine pregnancy test on Day 1, prior to administration of IP.

Women of CBP must also use an acceptable method of contraception from prior to Day 1 through Day 183 End of Study Visit. Acceptable methods include highly effective forms of contraception: hormonal contraceptives (eg, implants, pills, patches) containing combined estrogen and progestogen, or progestogen-only initiated \geq 30 days prior to dosing or IUD inserted \geq 30 days prior to dosing or use of double barrier type of birth control (male condom with female diaphragm, male condom with cervical cap). Abstinence is acceptable only for adolescents (12 to <18 years of age) who are not sexually active.

Note: Contraception requirements do not apply for participants in exclusively same-sex relationships and these participants should have no plans to become pregnant by any other means for the duration of the study.

The investigator must confirm that contraception methods (eg, hormonal contraceptive or intrauterine device) were initiated \geq 30 days prior to Day 1 to be considered fully effective.

For female participants who are postmenopausal, documented FSH level of \geq 40 mIU/mL must be obtained. If the FSH is <40 mIU/mL, the participant must agree to use an acceptable form of contraception (see above).

The investigator must report any pregnancies as described in Section 7.3.1.

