4 SELECTION AND WITHDRAWAL OF PARTICIPANTS

4.1 Inclusion Criteria

Participants must meet all the following criteria to be enrolled:

- 1. Able and willing to provide informed consent (and assent, as applicable) voluntarily signed by participant (and guardian, as applicable).
- 2. Males or females, 12 to <65 years of age.
- 3. Generally healthy, in the opinion of the investigator, based on medical history, physical examination, and screening laboratory assessments.
- 4. Women who are either:
 - Not of CBP: pre-menarche, surgically sterile (at least six weeks post bilateral tubal ligation, bilateral oophorectomy, or hysterectomy), or postmenopausal (defined as a history of ≥12 consecutive months without menses prior to randomization in the absence of other pathologic or physiologic causes, following cessation of exogenous sex-hormonal treatment).

or:

- ii. Meeting all the below criteria:
 - Negative serum pregnancy test at Screening Visit
 - Negative urine pregnancy test immediately prior to dosing at Day 1
 - Use one of these acceptable methods of contraception (if women of CBP) for the duration of participation:
 - Hormonal contraceptives (eg, implants, pills, patches) initiated ≥30 days prior to dosing
 - Intrauterine device inserted \geq 30 days prior to dosing
 - Double barrier type of birth control (male condom with female diaphragm, male condom with cervical cap)
 - Abstinence is acceptable only for adolescents (12 to <18 years old) who are not sexually active.

Note: See Section 3.3.7 for this study's list of acceptable method of contraception.

Note: Contraception requirements do not apply for participants in exclusively same-sex relationships and these participants should have no plans to become pregnant by any other means for the duration of the study.

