5.2.1 Screening (Visit 1, within 30 days of Day 1)

Eligible participants will first undergo informed consent counseling. Once informed consent has been obtained, participants will undergo a Screening Visit to ascertain their eligibility in this study within 30 days prior to Day 1. The Screening Visit assessments will include:

- Informed consent (and informed assent, as applicable) (Section 11.1).
- Review of eligibility criteria (Section 3.3.1, Section 4.1, Section 4.2).

- Medical history (including presence of joint pain) (Section 3.3.2).
- Demographics (date of birth, race, ethnicity, and sex of participant) (Section 3.3.2).
- Prior and current medications (Section 3.3.2, Section 5.3).
- Vital signs (blood pressure, heart rate, respiratory rate, and temperature) as well as height and body weight (for BMI calculation) (Section 3.3.4).
- Complete physical exam (general appearance, eyes-ears-nose-throat, head-neck, lungs-chest, heart, abdomen, musculoskeletal, lymph nodes, skin, extremities, and neurological assessment) (Section 3.3.3).
- Blood collection for laboratory viral marker testing (HBsAg, HCV antibody [if HCV antibody is positive, HCV RNA testing can be performed], HIV-1/HIV-2) (Section 3.3.5).
- For women of CBP: blood sample for serum pregnancy test (Section 3.3.5, Section 3.3.7).
- For postmenopausal women: blood sample for FSH levels (Section 3.3.5, Section 3.3.7).
- Urine sample for toxicology (per investigator's [or designee] discretion) (Section 3.3.5).

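### A postmenopausal woman with FSH below 40 mIU/mL must use contraception but has no clear pregnancy-test instruction, because criterion 4(i) has no FSH condition and Section 3.3.7 does not class her as of childbearing potential

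*Protocol*

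**What the plan says.** Criterion 4 offers women two routes into the study. Under 4(i), in the synopsis and again in Protocol 4.1, a woman is not of CBP if she is "postmenopausal (defined as a history of ≥12 consecutive months without menses prior to randomization in the absence of other pathologic or physiologic causes", with the further condition "following cessation of exogenous sex-hormonal treatment". No FSH value appears there. Under 4(ii) she must meet every listed item, including "Negative serum pregnancy test at Screening Visit", a negative urine test just before dosing, and contraception.

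Protocol 3.3.7 adds an FSH rule: "For female participants who are postmenopausal, documented FSH level of" at least 40 mIU/mL has to be obtained. For a lower value it says: "If the FSH is <40 mIU/mL, the participant must agree to use an acceptable form of contraception (see above". The same section opens its testing paragraph with "Women of CBP will undergo a serum pregnancy test at the Screening Visit" and a Day 1 urine test for the same group. Its next sentence makes a negative Day 1 urine test a condition of dosing and carries no CBP qualifier.

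The other procedural text keeps the two groups apart. Section 3.3.5 lists a "serum pregnancy test for women of CBP, and for FSH testing for postmenopausal women"; Section 5.2.1 has "For women of CBP: blood sample for serum pregnancy test"; Section 5.2.2 and the Schedule of Events also tie the test to women of CBP. SAP 2.2 presents FSH and the serum pregnancy test as alternatives at screening, and gives the Day 1 urine test to women of CBP.

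**The concern.** By asking for contraception when FSH is below 40, Section 3.3.7 treats the woman as possibly fertile. Criterion 4(i), which sees only her history, still counts her as not of CBP, and no sentence reconciles the two. The pregnancy tests follow CBP status, so the contraception rule reaches her while the test rule may not. Contraception agreed after a screening result does not show that she is not already pregnant on Day 1, which exclusion 1 requires. The serum and urine tests are the protocol's check on that. What is at stake is one participant-safety step before vaccination, not any analysis.

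**Working it through.** The plan gives no figure to reproduce. The check follows one woman through the text: at least 12 months without menses, no other cause, hormones stopped, screening FSH below 40 mIU/mL.

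1. **Eligibility route.** She meets every condition of 4(i). Routes 4(i) and 4(ii) are alternatives, so nothing obliges the site to consider 4(ii).
2. **Effect of the FSH result.** The only consequence stated in 3.3.7 is contraception. No sentence makes her of CBP, moves her to 4(ii) or orders a pregnancy test.
3. **Serum test.** Sections 3.3.5, 3.3.7, 5.2.1 and the Schedule direct it to women of CBP. As a 4(i) entrant she is not named.
4. **Urine test.** Section 5.2.2 and the Schedule direct it to women of CBP. The unqualified sentence in 3.3.7 follows directly on the women-of-CBP sentence. Read broadly it would cover her urine test; it would still say nothing about serum.
5. **The test items in 4(ii).** These carry no CBP wording of their own, but they apply only to a woman who enters by 4(ii).
6. **Other checks.** Exclusion 1 bars a pregnant woman, and eligibility is reverified on Day 1. Neither orders a test.
7. **Contraception as a substitute.** Screening is no more than 30 days before Day 1. Hormonal methods and IUDs must be in place at least 30 days before dosing. A woman who starts a method only after a low FSH result will therefore generally be left with double barrier unless she is rescreened. Whichever method she uses, starting it cannot exclude an existing pregnancy.
8. **Timing.** Criterion 4(ii) fixes the serum test at the Screening Visit, when the FSH sample is also drawn. The FSH result may arrive after the site has already decided that no pregnancy sample was needed.

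Cost per affected woman: 1 serum test + 1 urine test = 2 tests.

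Number affected = enrolled × share of women × share postmenopausal by history × share of those with FSH below 40. The documents give the first term (at least 3150) and none of the three shares, so no count is computed.

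**The case against.** The strongest reply is that the text as a whole already sends her to 4(ii). Criterion 4 is binary, and within it contraception appears only in 4(ii), marked there for women of CBP. An FSH of at least 40 has to be documented for a postmenopausal woman, so one below 40 has not been confirmed as such. The cross-reference in 3.3.7 leads back to a paragraph on women of CBP, which presents contraception as an addition to testing. The unqualified urine-test sentence points the same way. Exclusion 1, Day 1 reverification and the requirement in 4(i) that no other physiologic cause explains the amenorrhoea add protection, and the Laboratory Manual may say more.

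Much of this stands as evidence of intent: management under 4(ii) is probably what was meant, and many sites would arrive there. It does not close the gap. The cross-reference attaches to the form of contraception, not to testing; 3.3.7 states the consequence of a low FSH and stops at contraception; the urine sentence leaves serum untouched; and the remaining safeguards call for judgement, not a test. If 4(ii) was intended, saying so changes nothing for sites that already read it that way.

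A further objection is that an amendment may come late. SAP 5.1.2 and 5.6 describe rescreening and randomization problems in the past tense, so enrolment was under way and may have been well advanced. That does not show it had closed, but it is why a fallback is needed.

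**Conclusion.** The gap is real and minor. Followed literally, the protocol lets a woman whom it treats as possibly fertile be vaccinated without a pregnancy test. It should be corrected because the rules do not fit together, the literal path is the less safe one, and the correction is cheap.

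The reach is unknown. That it is small is an assumption: it depends on how many women meet 4(i) by history with FSH below 40, and on how many sites take the narrow reading. No endpoint, alpha or power figure is affected.

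A reader might infer more than this. The documents do not show that any woman was dosed untested. They do not forbid testing her, and they do not admit pregnant women, whom exclusion 1 bars. Nor does drawing the FSH and serum pregnancy samples at one visit create a conflict in itself, since a site can take both; what is missing is an instruction for a low FSH result that arrives afterwards.

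**What to change.** - In criterion 4(i), synopsis and 4.1, add a documented FSH of at least 40 mIU/mL to the definition of postmenopausal.
- In 3.3.7, state that a woman with FSH below 40 is treated as of CBP under 4(ii), with contraception and both pregnancy tests. Keep the existing exemption from contraception for women in exclusively same-sex relationships.
- Settle the timing of the serum test in one of two ways. Either take the serum pregnancy sample with the FSH sample at Screening for every woman entered as postmenopausal, or change the timing in 4(ii), 3.3.5, 3.3.7, 5.2.1 and the Schedule to *at Screening, or after the FSH result and before Day 1*. The second choice needs all of those places edited; otherwise a later test would not satisfy 4(ii) as written. Section 5.2.10 already allows an unscheduled visit for it.
- If enrolment has closed, use the FSH and pregnancy-test listing planned in SAP 9.4.1 to identify any woman with FSH below 40 who was dosed without a pregnancy test, and report the number.

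The cost is amendment wording plus two routine tests per affected woman, both of types already in the schedule. The first timing option instead adds one serum test for each postmenopausal woman, with the urine test added for those below 40. After enrolment has closed, the cost is one check of a listing that is already planned.
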